## Materials and methods:

A total of 30 implants of the same brand and type (M4 MIS Dentsply, Germany) were placed in15 partially edentulous volunteers in need of implantation in the mandible or maxilla or both. All cases were digitally planned using data from cone beam computed tomography, and the comparison of the planned and actual implant positions was performed using a medical image analysis software (blue sky plan 4). Post-op. CBCT was used for nine measurements representing the deviations in angles, implant shoulders and apexes. The outcome parameter was angular deviation (AD, degrees), crestal global deviation (CGD, mm), vertical linear deviation (VLD, mm), lateral linear deviation (LLD, mm), apical global deviation (AGD, mm), apical vertical deviation (AVD, mm), apical lateral deviation (ALD, mm), distance from maxillary sinus and distance from inferior alveolar nerve. Statistical analysis was performed using Fisher's exact test to compare the proportion between groups and Chi square test to test the relationship between two categorical variables.

Keywords: Countersink guided, Quasi experimental study, fully guided, Accuracy, partially edentulous.

**Trial registration:** Palestinian Health Research Council ethical approval attains from the Helsinki committee trial registration number (PHRC/HC/1242/23) at date of registration in it's meeting on 23/02/2023.

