#### **Data Collection procedure:**

#### **Analysis method:**

Free hand (countersink guided) and surgical guide surgeries were carried out by a parallel surgical kit (Dentsply®, MIS, M4, Germany), following the manufacturer's recommendations. The surgical guide surgeries were carried out using a dedicated (Dentsply®, MIS, M4 Germany) following the above-mentioned surgical plan. Both of the implants were performed for the same patient, on the same day and with the same devices. One implant per side was placed free hand, countersink guided and the other side with a computer-assisted implant guide.

With Blue Sky Plan 4 (Blue Sky Bio, Grayslake, IL, USA) software, the post-operative fixture was extracted as an STL file by segmentation the DICOM file of the CBCT taken after surgery used 3D slicer program as show in Figure 1.

Figure 1: show segmentation the DICOM file of the CBCT taken after surgery used 3D slicer program.

Then, the STL file post-operative fixture imported to Blue Sky Plan 4 program and superimposing with planned fixture on the CBCT on the planned implant location before surgery as presented in Figure 2.

Figure 2: show import the DICOM file post-operative fixture to Blue Sky Plan 4 program and superimposing with the CBCT which have the planned implant location before surgery.

More than twenty points marked on the two images using a point-based automatic image registration algorithm to ensure correspondence as show in Figure 3.

Figure 3 : aligned using a point-based automatic image registration algorithm.

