#### Measure the deviation for each parameter:

The definitions concerning accuracy outcome measures are as follows: The primary outcome was angular deviation defined as the angle closed by the principal axis of the planned implant and the principal axis of the inserted implant in degrees. The secondary outcomes were crestal global deviation; the distance between the center of the coronal end of the planned and the inserted implants in millimeters, apical global deviation; the distance between the apical endpoints of the planned and the inserted implants in millimeters, and vertical linear deviation ; the distance between perpendicular line on the hexagon of planned implant and another line draw parallel to it on the hexagon of actual implant in millimeters, lateral linear deviation; the distance between vertical line on the long axis of planned implant and another line draw parallel to it on the long axis of actual implant in millimeters, apical vertical deviation ; the distance between perpendicular line on the apex of planned implant and another line draw parallel to it on the apex of actual implant in millimeters, apical lateral deviation ; the distance between vertical line on the long axis of planned implant and another line draw parallel to it on the long axis of actual implant in millimeters, Two anatomical parameters were added to these ones : the distance from the inferior alveolar nerve (IAN) and the distance from the maxillary sinus (MS).

Primary outcome is Angular deviation of the final position to the planned implant position. Meanwhile, secondary outcomes are described by the following eight measurements.

Figure 4: Deviation parameters between the planned implant position (blue) and placed implant position (yellow): (a) Lateral Linear deviation (mm); (b) Vertical Linear deviation (mm); (c) Global Crestal deviation (mm); (d) Apical Lateral deviation (mm); (e) Apical Vertical deviation (mm); (f) Apical Global deviation (mm); a, Angular deviation (degree). (Ngamprasertkit et al., 2022)

The real measurements of the primary and secondary outcomes using Blue Sky Plan 4 Software are presented in Figure 5.

linear deviation (mm); (e) lateral linear deviation (mm); (f) crestal global deviation (mm); (g) apical vertical deviation (mm); (h) apical global deviation.

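### The nerve and sinus distances count as secondary accuracy outcomes, but the readable text ties neither to the planned implant nor to a landmark; if compared raw, they mix planned clearance with placement error.

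*Combined protocol and SAP*

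**What the plan says.** The section on measuring the deviation for each parameter defines angular deviation (primary) and six linear deviations (crestal global, apical global, vertical linear, lateral linear, apical vertical, apical lateral). Each definition contrasts the planned implant with the inserted or actual one. The Figure 4 caption covers the same seven as "Deviation parameters between the planned implant position (blue) and placed implant position (yellow"); the nerve and sinus distances are not among them.

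The text then continues "Two anatomical parameters were added to these ones" and names "the distance from the inferior alveolar nerve (IAN) and the distance from the maxillary sinus (MS"). It gives no planned reference, implant landmark or unit for either. The section goes on: "Meanwhile, secondary outcomes are described by the following eight measurements". The abstract states: "Post-op. CBCT was used for nine measurements representing the deviations in angles, implant shoulders and apexes", and its list of outcome parameters includes both distances.

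On design, the abstract describes 15 patients and 30 implants, with patients "in need of implantation in the mandible or maxilla or both". Under Analysis method: "One implant per side was placed free hand, countersink guided and the other side with a computer-assisted implant guide". The Data Analysis section names t tests (independent or paired) or nonparametric tests for scale variables. It mentions no adjustment for planned distance.

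**The concern.** The stated aim is accuracy, meaning how close the placed implant comes to the plan. A post-operative distance to the nerve or sinus does not measure that alone. An implant placed exactly as planned, but planned close to the nerve, reads as closer than a badly misplaced implant that was planned with generous clearance.

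Each patient contributes one site per technique, on opposite sides, and each site has its own planned clearance. Pairing by patient removes what the two sites share, but not the difference in planned clearance between them. The documents do not say how the side for each technique is chosen, so balance of planned clearance is not assured. What is at stake is the interpretation of two of the eight secondary outcomes.

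**Working it through.** **Counts.** One primary outcome, six linear deviations and two anatomical distances. Secondary: 6 + 2 = 8. Total: 1 + 6 + 2 = 9. Both agree with the document, and only if the two distances are included. Outcomes defined against the plan: 1 + 6 = 7.

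**Model, if raw distances are compared.** Placed distance = planned distance + placement error. Let planned distance have SD s and within-patient correlation r between the two sites, and let error have SD e and be independent of planned distance. For the paired difference between techniques:

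- SD(raw) = √[2s²(1 − r) + 2e²]
- SD(signed placed-minus-planned) = e√2
- share of raw variance due to planned clearance = 2s²(1 − r) / [2s²(1 − r) + 2e²]

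**Assumed inputs (none is in the documents).** s = 1, 2, 3 mm; r = 0.5, 0.9; e = 0.5, 1 mm; k = 8 pairs within one jaw (about half of 15); paired t test, two-sided 5%.

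**Share of variance.** Lowest (s = 1, r = 0.9, e = 1): 0.2/2.2 = 9.1%. Highest (s = 3, r = 0.5, e = 0.5): 9/9.5 = 94.7%.

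**Rejection rates.** Noncentral t with 7 df and noncentrality d√8/SD. For d = 1 mm, the raw test has its lowest rate at SD √11 = 3.317 (noncentrality 0.853, 11.5%) and its highest at SD √0.7 = 0.837 (noncentrality 3.381, 82.5%). The signed test has noncentrality 2.0 (e = 1, 40.8%) or 4.0 (e = 0.5, 92.7%). Rates for the absolute difference are from simulation, 40,000 replicates per cell.

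| Situation, k = 8 | Raw | Signed | Absolute |
|---|---|---|---|
| Equal accuracy, planned clearance differs by 0.5 mm | 6.6–31.0% | about 5% | about 5% |
| Equal accuracy, planned clearance differs by 1.0 mm | 11.5–82.5% | about 5% | about 5% |
| Mean error shift 0.5 mm, clearance balanced | 6.6–31.0% | 14.0–40.8% | about 5–14% |
| Mean error shift 1.0 mm, clearance balanced | 11.5–82.5% | 40.8–92.7% | about 14–74% |
| Mean error zero, error SD 0.5 v 1.5 mm | about 5% | about 5% | about 53% |
| Mean error zero, error SD 0.5 v 1.0 mm | about 5% | about 5% | about 26–27% |

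The raw figures in rows 1 and 3, and in rows 2 and 4, are identical because the raw test cannot tell a clearance difference from an error shift of the same size.

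**Which difference should lead.** Over the 24 mean-shift cells (2 shifts × 3 values of s × 2 of r × 2 of e), the signed difference beats raw in all 24. This follows from the formulas, since e√2 is smaller than SD(raw) whenever r < 1. Raw beats the absolute difference in 15 of 24. Example (shift 0.5 mm, s = 1, r = 0.9, e = 0.5): raw 31%, signed 41%, absolute 14%. The absolute difference is the only one of the three that responds to scatter alone. For that, with SD 0.5 v 1.5 mm, its power is about 23% at 5 pairs and 91% at 15.

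**Independent t test instead.** With 15 implants per technique, e = 1 mm and a planned-clearance difference of 1 mm, the raw test rejects in 13% (s = 3) to 46% (s = 1) of trials. The figures change with the test but the pattern does not.

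**The case against.** The strongest objection is that the gap may come from the lost figure. The document says: "The real measurements of the primary and secondary outcomes using Blue Sky Plan 4 Software are presented in Figure 5". The surviving caption starts part-way through the item before (e) and ends at (h). It shows a linear deviation, then lateral linear, crestal global, apical vertical and apical global deviation. Angular deviation, apical lateral deviation, the nerve distance and the sinus distance are not visible: four outcomes for three lost panels, (a) to (c). If each lost panel showed one outcome, at least one showed the nerve or the sinus, perhaps with a landmark or planned reference. A lost panel could also have been an overview. This stands as a limit on the point.

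Second, the section heading and the abstract both speak of deviations, and the abstract says planned and actual positions were compared. These lean towards a difference from plan. They are general labels, however: the abstract's sentence refers to angles, shoulders and apexes, and no readable sentence says placed minus planned for either structure.

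Third, apical vertical and apical global deviation already measure departure from plan at the apex. Where the structure lies beyond the apex, a difference from plan partly repeats them. That is fair, but a signed difference adds direction, and raw clearance keeps its value as a description of proximity.

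A reader might go further and infer that the trial does compare raw distances, or that the comparison is biased. The documents support neither. No sentence says that raw values are compared, and nothing shows planned clearance differing by technique. If it is balanced, the raw comparison is unbiased and only noisier.

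**Conclusion.** The point holds conditionally and is minor. In the readable text, two of the eight secondary accuracy outcomes lack the planned reference and the landmark needed to interpret them as accuracy. Taken literally, the wording gives a comparison that carries site differences in planned clearance as well as placement error. That costs precision in every case, and validity as an accuracy measure only if planned clearance differs by technique.

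The size cannot be derived from the documents. The wide ranges above (9–95% of variance; 11.5–82.5% rejection for a 1 mm clearance difference) rest wholly on assumed SDs, correlations, number of pairs and choice of test. They show the mechanism, not its extent in this trial. Angular deviation and the six linear deviations are unaffected, because each is defined against the plan.

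**What to change.** For each implant, read the planned and the placed distance from one named landmark, the same on both fixtures, in the superimposed planning file that already exists: nerve distance for mandibular implants, sinus distance for maxillary implants. Then:

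- Compare the signed placed-minus-planned difference between techniques with a 95% CI (negative = closer to the structure than planned). Pair where both of a patient's sites are in that jaw, and give n per jaw.
- Report the absolute difference as a supplementary measure of scatter, which a signed mean near zero would hide.
- Report planned distance by technique, so that any imbalance is visible.
- Keep the raw post-operative distance as a descriptive measure of proximity.

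If a difference from plan was already intended, it is enough to say so, and to name the landmark, where the two distances are introduced.

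The cost is one extra reading per implant plus wording, with no new imaging or patients. The drawbacks are two summaries per structure and small samples within each jaw: on the assumptions above, power with 8 pairs is often below 80% even for the signed difference.

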#### **Data Analysis**

The researcher employed the Statistical Package for the Social Sciences (SPSS) version 22 program for both data entry and statistical analysis. The data analysis process comprised two stages: first, descriptive analysis to summarize the data, followed by an inferential analysis that elucidated the relationships between the variables under investigation. Also, the Central tendency measures were performed to describe the collected data from patients. Exact Fisher's Test, Chi-square Test and Independent t-Test were used to examine the possible relationship between variables. The confidence interval was considered at 95% and a margin of error 5%. P-value less than 0.05 was considered to indicate a statistically significant difference.

Categorical outcomes were presented as absolute and relative frequencies. A bivariate analysis using Independent t-Test, or Fisher's exact test when application conditions were not achieved, was used to compare the groups. Differences between groups of scale variables were explored using parametric (Student's t test for independent or paired samples) or nonparametric tests. Chi square test was used to test the relationship between two categorical. In the present study the Independent t-Test, Fisher's exact test and Chi square test as well as median were used where the data was classified nonparametric.

Abbreviations:

Symbol	Description
СВСТ	Cone Beam Computed Tomography
CAD	Computer Aided Design
CAM	Computer-aided manufacturing
CAI	Computer Assisted Inspection
DICOM	Digital Imaging and Communications in Medicine
GIS	Guided Implant Surgery
STL	Standard Tessellation Language OR Standard Triangulated
AD	Angular deviation
CGD	crestal global deviation
VLD	Vertical Linear Deviation
LLD	Lateral Linear Deviation
AGD	apical global deviation
ALD	Apical Lateral Deviation
MS	Maxillary Sinus
IAN	Inferior Alveolar Nerve
s-CAIS	Static computer-assisted implant surgery
IOS	Intra oral scan
3D	Three-dimensional
FG	Fully guided
FH	Freehand
CS	Countersink
SD	Standard deviation
AVD	apical vertical deviation
FHM	free hand method
SGM	surgical guide method
FH	free hand

SG	surgical guide
PG	pilot guide
FG	fully guided

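### No test is assigned to angular deviation, and the independent t-test named for comparing the groups ignores the 15 within-patient pairs of the split-mouth design

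*Combined protocol and SAP*

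**What the plan says.** The abstract's Materials and methods paragraph gives the numbers: "A total of 30 implants of the same brand and type (M4 MIS Dentsply, Germany) were placed in15 partially edentulous volunteers". The Analysis method section gives the layout: "Both of the implants were performed for the same patient, on the same day and with the same devices", and "One implant per side was placed free hand, countersink guided and the other side with a computer-assisted implant guide". The section on measuring deviation sets the primary endpoint: "The primary outcome was angular deviation defined as the angle closed by the principal axis of the planned implant". It is a continuous quantity in degrees.

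The Data Analysis section names the independent t-test three times:

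- in a general list of tests, together with Fisher's exact and chi-square;
- as the test for the group comparison: "A bivariate analysis using Independent t-Test, or Fisher's exact test when application conditions were not achieved, was used to compare the groups";
- in the closing statement of what this study used: "the Independent t-Test, Fisher's exact test and Chi square test as well as median were used where the data was classified nonparametric".

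A paired test appears once, inside a list of options for scale variables: "Student's t test for independent or paired samples", or nonparametric tests. No rule for choosing is given. The abstract lists only two categorical tests: "Statistical analysis was performed using Fisher's exact test to compare the proportion between groups and Chi square test".

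**The concern.** A split-mouth design lets each patient serve as his or her own control. The analysis has to use the within-patient difference to gain from that, and its standard error has to reflect the pairing to be correct. The independent t-test does neither.

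The text also leaves the primary analysis open. Independent, paired, nonparametric and categorical tests are all mentioned, and none is linked to angular deviation. The closing list has no paired test, and it places a parametric test under data described as nonparametric. Fisher's exact test, offered when the t-test's conditions fail, cannot compare a continuous angle. The abstract names no test for a continuous outcome at all. A reader cannot tell whether the pairing is used, and the choice could be made after the data are seen.

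**Working it through.** **Inputs from the documents.** 30 implants / 15 patients = 2 per patient, one per method, hence n = 15 pairs. Significance is at p < 0.05. The plan reports no sample-size or power figure, so there is none to reproduce.

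**Assumptions.** Exactly two implants in every patient, a two-sided test, normal data, equal SDs σ in the two methods, a true difference of 0.8σ, and within-patient correlation ρ from −0.3 to 0.7. The documents give no value for σ, ρ or the difference.

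**Critical values.** Independent test, 28 df: t = 2.048. Paired test, 14 df: t = 2.145. Ratio 2.048/2.145 = 0.955.

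**Why the independent test is miscalibrated.** The true variance of the mean difference is 2σ²(1−ρ)/15. The independent test estimates it as 2s²/15. Its pooled variance s² is distributed as σ²[(1+ρ)A + (1−ρ)B]/28, with A and B independent chi-square variables on 14 df, so s² averages σ² whatever ρ is. The standard error is therefore off by a factor of about 1/√(1−ρ): 0.88 at ρ = −0.3, 1.20 at 0.3, 1.41 at 0.5 and 1.83 at 0.7.

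**Type I error and power.** For the independent test, the normal tail probability was integrated over the distribution of s². Paired power comes from the noncentral t on 14 df with noncentrality 0.8/√(2(1−ρ)/15), which is 2.19, 2.62, 3.10 and 4.00 at ρ = 0, 0.3, 0.5 and 0.7. The paired test holds 5% at every ρ.

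**Width of the 95% confidence interval, independent over paired.** The ratio is 0.955/√(1−ρ).

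| ρ | Type I error, independent | Power, independent | Power, paired | CI width ratio |
|---|---|---|---|---|
| −0.3 | 8.4% | 55.5% | 43.2% | 0.84 |
| 0 | 5.0% | 56.2% | 53.2% | 0.96 |
| 0.1 | 4.0% | 56.5% | 57.5% | 1.01 |
| 0.3 | 2.1% | 57.3% | 68.3% | 1.14 |
| 0.5 | 0.8% | 58.6% | 82.1% | 1.35 |
| 0.7 | 0.1% | 60.6% | 96.0% | 1.74 |

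At ρ = −0.3 the independent test's higher power and narrower interval reflect its inflated error rate and are not a real gain.

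**Break-even.** The paired interval is the narrower one once ρ exceeds 1 − 0.955² = 0.088.

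**Unequal SDs.** If one method's SD is twice the other's, the width ratio becomes 0.955 × √(5/(5−4ρ)) = 1.10, 1.23 and 1.44 at ρ = 0.3, 0.5 and 0.7.

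**Nonparametric alternative.** Simulated power of the Wilcoxon signed-rank test (15 pairs, exact critical values W ≤ 25 or W ≥ 95) at the same 0.8 SD difference is about 66%, 80% and 95% at ρ = 0.3, 0.5 and 0.7.

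**The case against.** The strongest reply is that the sentence naming the independent t-test for the group comparison follows directly after one about categorical outcomes and falls back on Fisher's exact test, so it may be a garbled sentence about categorical data. The next sentence covers scale variables, a class that includes angular deviation, and it allows a paired test. On that reading the plan is ambiguous rather than wrong.

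This does not rescue the plan. A t-test cannot compare categorical outcomes, and the closing list of tests used in this study omits any paired test without help from the disputed sentence. The option for scale variables offers independent and paired forms with no rule for choosing.

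Some of the reply stands. That the independent t-test is the primary analysis is an inference, because no sentence says so. The abstract ties its two tests to proportions and categorical variables, so it omits a test for the angle and does not assign a wrong one. The size of the loss rests wholly on assumed values, and at correlations of 0 to 0.1 the two tests nearly coincide. With positive correlation a significant independent t-test would still stand.

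**Conclusion.** The concern holds. The design yields 15 pairs, the test named for comparing the groups ignores them, and no test is tied to the primary outcome. Following the text as written gives a miscalibrated standard error, p-value and confidence interval for angular deviation unless the within-patient correlation is exactly zero.

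The direction depends on that correlation. If it is positive, the test is conservative: at correlations of 0.3 to 0.7 it gives up about 11 to 35 points of power for a 0.8 SD difference (68.3 − 57.3 and 96.0 − 60.6), and its interval is 14% to 74% wider, or 10% to 44% wider if one SD is twice the other. If it is negative, type I error exceeds 5%. These sizes are conditional on the stated assumptions. The mismatch between design and test does not depend on them. This must be fixed, because it concerns the primary analysis of a 15-patient study.

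**What to change.** In the Data Analysis section, name one test for angular deviation: the paired t-test on the within-patient difference (free hand/countersink minus fully guided), reported as a mean difference with 95% confidence interval on 14 df. Use the same test for the other between-method deviations. Name the Wilcoxon signed-rank test as the nonparametric alternative and state in advance when it applies; otherwise the present ambiguity returns.

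Remove the independent t-test, Fisher's exact test and chi-square test from the between-method comparisons. If any categorical between-method comparison is kept, it needs a paired method too, such as McNemar's test. Make the abstract say the same.

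The nerve and sinus distances each apply to one jaw only, and patients may have implants in either jaw or both. State the number of complete pairs for each of these two outcomes, since 14 df holds only with all 15. A mixed model with a random patient intercept and a method effect is optional as a sensitivity analysis. Adding side or jaw terms would make it a different, adjusted analysis.

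The cost is wording in two sections, with the same data and software. The paired test loses about 3 points of power if the correlation is truly zero (56.2% against 53.2%). Both sections are written in the past tense, so if the data have already been analysed, this is a re-analysis and should be declared as one.

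### The plan contradicts itself on how the continuous accuracy outcomes are tested: the only named alternatives to the t-test are tests for counts, and no cut-point is given

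*Combined protocol and SAP*

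**What the plan says.** **Outcomes.** The section on measuring the deviations defines the primary outcome as "the angle closed by the principal axis of the planned implant and the principal axis of the inserted implant in degrees". The secondary outcomes are six deviations in millimetres, for example "the distance between the center of the coronal end of the planned and the inserted implants in millimeters", and two anatomical distances (to the inferior alveolar nerve and to the maxillary sinus). No accuracy outcome is defined as a category, and no threshold is given for any of them.

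**Design.** The abstract reports "A total of 30 implants of the same brand and type" in 15 patients, and the Analysis method section says "One implant per side was placed free hand, countersink guided and the other side with a computer-assisted implant guide". That gives 15 within-patient pairs.

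**Tests.** Four statements bear on how the groups are compared:

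1. Data Analysis: "A bivariate analysis using Independent t-Test, or Fisher's exact test when application conditions were not achieved, was used to compare the groups".
2. Data Analysis, next sentence: scale variables may be compared with Student's t-test, independent or paired, or with nonparametric tests. None of the latter is named.
3. Data Analysis, closing sentence: the independent t-test, "Fisher's exact test and Chi square test as well as median were used where the data was classified nonparametric". The t-test stands at the head of that list, just before the quoted words.
4. Abstract, Materials and methods: "Statistical analysis was performed using Fisher's exact test to compare the proportion between groups", with chi-square for the relation between two categorical variables. No test for a continuous outcome is named there.

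Neither the Wilcoxon signed-rank test nor the Mann-Whitney test appears anywhere.

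**The concern.** Fisher's exact and chi-square tests work on counts. To use either on an angle or a distance, the analyst must first cut the measurement at a threshold, and the plan supplies none. The closing Data Analysis sentence adds a second fault: it lists a parametric test among those used for data classed as nonparametric.

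Two analysts working from this text could therefore test angular deviation in different ways: an unpaired t-test, a paired t-test, an unnamed rank test, or a proportion above a threshold of their own choosing. If the last is done, the p-value depends on the threshold, power is lost, and the result is not a difference in degrees or millimetres, which is what a comparison of accuracy needs. With 15 patients there is little power to spare. The fault would exist even if the groups were independent, so it is separate from whether the analysis respects the pairing.

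**Working it through.** The plan gives no sample-size calculation, effect size, SD, within-patient correlation or cut-point, so there is no figure of its own to reproduce. The check asks what follows if statement 1 is taken literally for a continuous outcome.

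**Inputs from the documents:** 30 implants, 15 patients, one implant per technique per patient, significance level 0.05 (taken as two-sided, since the sidedness is not stated).

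**Assumed inputs:** lognormal deviations with log-scale SD 0.5; freehand-to-guided ratio 1.5 or 2.0, which is ln(1.5)/0.5 = 0.81 or ln(2)/0.5 = 1.39 SD on the log scale; within-patient correlation 0; cut at the pooled median.

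**Step 1. What Fisher's test needs.** With a pooled-median split of 15 v 15, all margins are 15, so P(X = k) = C(15,k)² / C(30,15), with C(30,15) = 155,117,520.
- 11 v 4: the upper tail is (1365² + 455² + 105² + 15² + 1²)/155,117,520 = 0.0134; doubled, p = 0.027.
- 10 v 5: adding 3003² gives 0.0716; doubled, p = 0.143.

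So at least 11 of 15 against 4 of 15 is needed.

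**Step 2. Power at correlation 0** (simulation, 20,000 runs; repeated runs agree to within about 2 points).

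| Test | Ratio 1.5 | Ratio 2.0 |
|---|---|---|
| Fisher's exact, pooled-median split | about 32% | about 78% |
| Wilcoxon signed-rank | about 50% | about 91% |
| Independent t-test on the raw values | about 53% | about 93% |

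The loss against signed-rank is about 18 and 13 points. With zero correlation none of it comes from ignoring the pairing. Under no true difference, Fisher's test at this split rejects in about 2.6% of runs rather than 5%.

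**Step 3. Correlation 0.3.** At ratio 1.5, signed-rank has about 64% and Fisher's about 30%, a gap of 34 points. The unpaired Mann-Whitney test has about 54%, so 64 − 54 = 10 points come from ignoring the pairing and 54 − 30 = 24 from cutting the data.

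**Step 4. Dependence on the cut-point.** This uses a second set of assumptions: lognormal, log-scale SD 0.6, difference 1.06 SD on the log scale (a ratio of exp(0.636) = 1.89), correlation 0, 10,000 runs. Signed-rank has 71% and the independent t-test 72%. Fisher's test has:
- 53% at the pooled median;
- 44% at a fixed cut midway between the two group medians on the log scale;
- 38% to 39% at either group's median;
- about 6% at a cut 1 SD above the worse group's median.

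The same data can thus give very different power depending on a number the plan does not state.

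**The case against.** The strongest reply is that the documents nowhere say a deviation is dichotomised. The abstract ties Fisher's test to proportions and chi-square to categorical variables, and the Data Analysis section repeats the latter. The sentence that makes Fisher's the fallback comes straight after one on presenting categorical outcomes, so it may be a garbled rule for categories. The only sentence that names the scale of these outcomes allows t-tests or nonparametric tests. The closing sentence, read in full, still includes a t-test.

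Most of this stands, and it limits the point. A reader might infer that the plan definitely tests angular deviation as a proportion, or that the closing sentence overrides the one on scale variables. The documents support neither: they give no order of precedence. A reader might also infer that the fallback is bound to be used, with a cut-point picked after the data are seen. Skewness is plausible for unsigned deviations, but nothing in the text says either thing happened. Nor does skewness by itself cost the first-named test its power: in step 2 the independent t-test does about as well as signed-rank.

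What the reply does not do is tell the analyst which test applies to angular deviation when normality is doubted. Statements 1 and 3 name tests for counts, statement 2 names no rank test, and the abstract names no test for a continuous outcome. The contradiction remains on any reading.

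**Conclusion.** The point holds as a contradiction and a gap. The Data Analysis section and the abstract do not agree on how the continuous outcomes are tested, and the only alternatives to the t-test that they name cannot be applied to those outcomes without an unstated cut-point.

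The cost is conditional. If the Fisher's fallback is followed at a pooled-median split, power falls by roughly 13 to 18 points against signed-rank in the zero-correlation scenarios of step 2, and by more at a fixed cut as in step 4. If the t-test is kept, that loss does not arise. The power figures rest on assumed distributions, ratios, correlation and cut-points. The textual conflict rests on no assumption.

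**What to change.** Replace three sentences with one pre-specified rule that has no data-driven switch: in Data Analysis, the fallback sentence ("A bivariate analysis using Independent t-Test, or Fisher's exact test when application conditions were not achieved, was used to compare the groups") and the closing sentence that contains "Fisher's exact test and Chi square test as well as median were used where the data was classified nonparametric"; in the abstract, the statistics sentence. Suggested wording:

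> Angular deviation and the other deviation outcomes are analysed as continuous and are not dichotomised. The within-patient difference (freehand minus guided) is tested with the Wilcoxon signed-rank test and reported with the Hodges-Lehmann estimate and 95% CI.

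The general sentence on scale variables should then be cut or made to point to this rule; otherwise the choice of test stays open.

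Analyse the nerve and sinus distances as continuous too, using pairs only where both implants in a patient have that measurement. The abstract describes "partially edentulous volunteers in need of implantation in the mandible or maxilla or both", so there may be fewer than 15 such pairs for each. Keep Fisher's and chi-square tests only for truly categorical variables.

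The cost is wording in two places and a short re-analysis of measurements already taken on a continuous scale. No new data are needed. The documents are written in the past tense, so if results have already been seen, the change should be dated and the report should say so.
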